(B) diabetes incidence and level of cardiometabolic risk factors (2-hour glucose during OGTT, HbA1c, waist circumference, body mass index, systolic and diastolic blood pressure, serum triglycerides, HDL- and LDL cholesterol, Apo-B, Apo-A1, cortisol, ACTH, insulin (fasting and 2h post OGTT), glucagon (fasting and 2h post OGTT), C-reactive protein, estimated GFR, Creatinine clearance) (*secondary outcome measures*) in 800 individuals (400 in each treatment arm, see power calculation below). Similar to previous studies on e.g. prevention of high cholesterol, we selected the *difference in continuous change of fasting glucose as the primary outcome*, rather than dichotomous outcome of new-onset diabetes. The rationale is that a difference of glucose reduction in active vs control treatment (for example 0.5 mM) would be equally important when being 6.3 vs 6.8 mM or 7.1 vs 7.6 mM, without “crossing” the diagnostic threshold for diabetes (7.0 mM), as when the same 0.5 mM difference is 6.7 vs 7.2. Thus, individuals with type 2 diabetes will not be excluded (unless on insulin therapy) except in the analyses of the secondary outcome of new-onset diabetes. We expect the proportion of participants with diabetes to correspond to the prevalence in the population (i.e. approximately 4-6%).

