### 3.3 Sample size

The primary outcome parameter is the difference between active (=extra water) and control treatment in the change of fasting plasma glucose between baseline and 12 months. We use prior effect estimates from the largest RCT for diabetes prevention study in Europe, i.e. the Finnish Diabetes Prevention Study (FDPS) (New Engl J Med 2001;344:1343-50), which compared individual life style counselling (active treatment) with general oral and written life-style advice (control treatment) in relation to risk of new onset type 2 diabetes and change of plasma glucose concentration and found a 58% decreased relative risk of diabetes. After 12 months, the fasting glucose in the active treatment group was reduced by  $4 \pm 12$  mg/dL vs a  $1 \pm 12$  mg/dL increase in the control group with the mean difference of 5 mg/dL of the 12-month change of fasting glucose being highly significant ( $P < 0.001$ ).

To obtain sufficient statistical power to detect a clinically significant effect size, we base the power calculation on an effect of water vs control that is at least 50% of what is considered an epoch changing effect of lifestyle i.e., the difference observed in the FDPS, while assuming the standard deviation for the change ( $s = 0.67$  mmol/L) as observed in FDPS. To be able to detect  $\geq 50\%$  of that effect (a difference of 2.5 mg/dL = 0.14 mmol/L between treatments in 12-month change) we need 319 evaluable subjects in both the active and control treatment group at a power of 80% and a 2-tailed significance level of =0.05, a total of 638 evaluable subjects. As the glucose measurement in the study used a more recent and exact method, the standard deviation of the change of glucose was recalculated by the DSMB in October 2022 from the first completed 357 study participants ( $s = 0.58$  mmol/L). With this smaller standard deviation, the power (with all other assumptions unchanged) was 270 evaluable subjects per group, i.e.  $n=540$  evaluable subjects in total. When also taking into account a dysbalance (with slightly higher drop-out rate in subjects in the intervention group), a total of 544 evaluable subjects were estimated to be needed for 80% power.

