**OR Delta 24h UVol (Baseline vs. 3 months, 6 months, 9 months and 12 months):**

- Control Group: Those with an increase in delta 24h UVol not greater than 500 mL from baseline.
- Intervention group: Those with an increase in delta 24h UVol of at least 1000 mL from baseline.

Furthermore, all individuals attending a clinic study visit (V3, V6 or V8) in a non-fasted state will be excluded from the per protocol analyses. Some other protocol deviations let to exclude patients are detailed in Section 5.1.2

Missing data

Missing data on outcomes (i.e. change of fasting glucose and the secondary cardiometabolic measures) will not be imputed, so subjects with missing data on outcome parameters will not be included in analysis of the respective outcome. For each of the outcomes, the maximum number of subjects will be included (e.g. if there are n=544 evaluable subjects for fasting glucose change, all of these will be included even if there are less evaluable subjects for any other cardiometabolic outcome parameter).

Given the randomized nature of the study, we will not perform any adjustments (which in turn can be affected by missing data on the covariates adjusted for) with three exceptions: (1) As detailed in “statistics” we will include adjustment for the baseline value of the outcome parameter in question (e.g. the change of glucose outcome will be adjusted for the baseline value of glucose). The motif of this adjustment is to minimize bias related to regression towards the mean. (2) As the randomization is stratified by sex, this covariate will be included in all outcome analyses. (3) If clinically significant/meaningful treatment group differences appear in baseline values of age, BMI or diabetes status in any outcome analysis, we will add a sensitivity outcome analysis in which we adjust for such baseline differences. Any missing values for these covariates will be imputed to obtain the same number of evaluable subjects in non-adjusted and adjusted analyses. The technique we propose is Multiple Imputation by Chained Equations (MICE) with subsequent application of Rubin’s rule to combine results from different imputations. We will base the analyses on 20-30 imputed data sets. For this analysis we will use SAS PROC MI in combination with PROC MIXED/PROC GLM and PROC MIANALYZE.

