### 5.6.2 Analysis of primary outcome parameters

The primary analysis (intention-to-treat) will compare the between study groups (intervention vs control treatment) LS-means differences on the changes from baseline to 12 months and from baseline to 6 months in fasting plasma glucose. The main analysis will be based on a linear mixed model with fasting plasma glucose change from baseline to study visits where it is measured during the study (6 and 12 months) as dependent variable. This model produces unbiased estimates under the assumption that missing data are missing at random. The model will be adjusted (through fixed effects) for sex (because of the stratified randomization), baseline value of fasting plasma glucose, treatment, study visit and interaction between treatment and study visit. We will in the mixed regression analysis model within-patient correlation to decrease exponentially with number of days between measurements or through an AR(1) model. The choice of correlation structure specifies the variance-covariance matrix in the mixed regression model. The choice of covariance structure rests on principles of parsimony, simplicity and prior beliefs, rather than post-analysis testing. Model assumptions will be assessed through visual inspection of plots of suitable regression residuals. The estimated LS-mean differences between treatment levels for the change in fasting plasma glucose from baseline to 12 months and baseline to 6 months, the corresponding 95% confidence intervals (CIs) and p-values will be provided. The same analyses will be conducted on the imputed data set (see “Missing Data” sub-section under section 4.1) and the per protocol data set. The analyses will be conducted using SAS PROC MIXED.

Sensitivity analysis as described in Section 4.1, part “Missing Data” could be performed. Conclusions regarding the inclusion of baseline characteristics in the linear mixed model will be based on clinical significances.

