## **7 Changes in the SAP with respect to the protocol**

SAP Section	Change	Rationale
3.3	Sample size	The reason for the recalculation is that the instruments used are more accurate in the measurements than the instruments used in the Finnish Diabetes Prevention Study (FDPS). The pooled standard deviation of delta fasting plasma glucose (mmol/L) at month 12 is 0.58.

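### The primary model leaves out baseline diabetes status as a fixed effect: the test is valid and adequately powered, but some precision goes unused

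*SAP*

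**What the plan says.** SAP section 5.6.2 gives the primary analysis as a linear mixed model of change in fasting glucose at 6 and 12 months: "The model will be adjusted (through fixed effects) for sex (because of the stratified randomization), baseline value of fasting plasma glucose, treatment, study visit", together with the treatment-by-visit interaction. Within-patient correlation follows exponential decay or AR(1). No variance differs by diabetes status, diabetes status is not a term, and there is no baseline-by-visit term. The section says the covariance structure is chosen on prior grounds, not by testing after the analysis.

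Diabetes status appears in two other places. SAP section 4.1, under Missing data, allows a sensitivity adjustment: "If clinically significant/meaningful treatment group differences appear in baseline values of age, BMI or diabetes status". SAP section 6.6 lists it as a subgroup.

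The protocol's Outcome section keeps type 2 diabetes in the primary analysis unless treated with insulin. It argues that a given glucose difference matters equally on either side of the diagnostic threshold. On numbers it says: "We expect the proportion of participants with diabetes to correspond to the prevalence in the population (i.e. approximately 4-6" per cent.

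The planning figures are in SAP sections 3.3 and 7. The target is "a difference of 2.5 mg/dL = 0.14 mmol/L between treatments in 12-month change". On the SD: "The pooled standard deviation of delta fasting plasma glucose (mmol/L) at month 12 is 0.58". It "was recalculated by the DSMB in October 2022 from the first completed 357 study participants".

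**The concern.** Diabetes is defined largely by glucose, so the two groups start from different baseline means. Regression to the mean acts around each group's own mean. A single line through both groups treats a typical baseline value in a participant with diabetes as an extreme value that should fall a long way. The few participants with diabetes sit far out on the baseline axis and pull the common slope towards zero. The slope is then too flat for the other 94-96%, and residual variance is larger than it need be.

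The spread of glucose change may also be wider in diabetes, and a single residual variance then weights noisy and quiet values alike. At stake is the width of the confidence interval for a small target effect. Because the SAP rules out choosing the covariance structure after seeing results, any such term has to be written in beforehand.

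**Working it through.** **1. The plan's own figure.** With two-sided alpha 0.05, power 80%, difference 0.14 and SD 0.58: n per group = 2 × (1.96 + 0.8416)² × 0.58² / 0.14² = 269.4, so 270, as stated. For 544 subjects split 46:54 (250 and 294), SE = 0.58 × √(1/250 + 1/294) = 0.0499 and power = Φ(0.14/0.0499 − 1.96) = 80.1%. The plan's figure reproduces.

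**2. Diabetes as a fixed effect.** The documents give no baseline means, SDs or slopes by diabetes status, so these are assumptions:
- share with diabetes p = 5%;
- baseline SD 0.5 mmol/L without diabetes and 1.5 with;
- baseline means 2.0 mmol/L apart;
- the same slope b of change on baseline within each group;
- the same mean change in each group;
- total SD of change 0.58 (variance 0.3364).

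Within-group baseline variance Vw = 0.95 × 0.25 + 0.05 × 2.25 = 0.35. Between-group variance = 0.05 × 0.95 × 2.0² = 0.19. Total Vt = 0.54. The single fitted slope is b × Vw/Vt = 0.65b, which is the attenuation. Residual variance is 0.3364 − b²Vw²/Vt with baseline glucose only, and 0.3364 − b²Vw once diabetes status is added.

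| Within-group slope b | Residual variance, baseline only | With diabetes term | Reduction | Power, before to after |
|---|---|---|---|---|
| −0.3 | 0.3160 | 0.3049 | 3.5% | 82.5% to 83.8% |
| −0.5 | 0.2797 | 0.2489 | 11.0% | 86.8% to 90.4% |
| −0.6 | 0.2547 | 0.2104 | 17.4% | 89.7% to 94.4% |

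With means 1.5 to 2.5 apart, the reduction is 2-5% at b = −0.3 and 12-22% at b = −0.6. Roughly 4-19% is a fair summary. The gain shrinks if glucose falls on average in diabetes. It vanishes if that fall equals the slope times the separation (for b = −0.5, 0.5 × 2.0 = 1.0 mmol/L), because one line then fits both groups.

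A simulation (3,000 trials per case, 544 subjects, 12-month outcome only) gave reductions of 3.5%, 10.9% and 17.2%. With an assumed effect of −0.5 in diabetes and −0.14 otherwise (b = −0.5), the mean estimate was −0.158 with or without the diabetes term, so the term does not reweight participants. The reduction in that case was about 8%.

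**3. Separate residual variance by diabetes status.** Again p = 5% and overall SD 0.58. For an assumed SD in diabetes s₁, the variance without diabetes is v₀ = (0.3364 − 0.05s₁²)/0.95. The precision-weighted variance is V = 1/(0.05/s₁² + 0.95/v₀), and the weight of diabetes is (0.05/s₁²) × V. The last column assumes an effect of −0.5 in diabetes and −0.14 otherwise.

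| SD in diabetes | Ratio of SDs | Share of total variance | Weight of diabetes | V/0.3364 | Power, common effect | Power if −0.5 in diabetes: planned, grouped |
|---|---|---|---|---|---|---|
| 0.58 | 1.0 | 5% | 5% | 1.000 | 80.1% | 88.6%, 88.6% |
| 1.0 | 1.8 | 15% | 1.6% | 0.929 | 82.9% | 88.6%, 85.7% |
| 1.5 | 3.1 | 33% | 0.5% | 0.733 | 90.6% | 88.6%, 91.3% |
| 1.8 | 4.2 | 48% | 0.3% | 0.573 | 96.0% | 88.6%, 96.2% |

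At ratios of exactly 2 and 3, power with a common effect is 83.9% and 90.1%. In the differential-effect case the planned model estimates 0.95 × 0.14 + 0.05 × 0.50 = 0.158 in absolute size. The grouped model at SD 1.5 estimates 0.142. In simulation (4,000 trials per scenario) type I error was 0.046-0.053 with grouped variances and 0.045-0.056 with one variance.

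**The case against.** The strongest reply is that nothing is broken. The single-variance test holds its type I error. The 0.58 SD comes from trial completers with no stated exclusion of diabetes, so the planned 80% appears to include their noise already. A reader might infer that the trial is underpowered, or that 4-6% of participants supply much of the noise and that the lost power can be recovered at no cost. The documents support neither inference. They give no SD by diabetes status, and a share near one third needs an SD ratio of about 3. Recovering that power by variance grouping is not free: it nearly removes from the estimate the participants the protocol deliberately keeps.

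The subgroup analysis in section 6.6 also covers much of this ground. At SDs of 1.0, 1.5 and 1.8 in diabetes, the non-diabetic subgroup alone has 82.3%, 90.4% and 95.9% power, close to the grouped model. Only about 22-33 of 544 participants (4-6%) would inform the second variance.

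All of this stands against variance grouping as the primary model. It does not answer the fixed-effect point, because that term leaves the weights alone. The SAP's worry about missing covariates has some force, but section 4.1 already plans to impute diabetes status when it is missing.

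**Conclusion.** This is a modest, worthwhile gain in precision; it does not correct an invalid analysis. Unconditional adjustment for baseline diabetes status would lower residual variance by roughly 4-19% under the assumed baseline means and slopes. That would narrow the confidence interval by about 2-10% (1 − √0.96 to 1 − √0.81). The gain may be smaller, and is nil if one line already fits both groups. The baseline-by-visit term is a minor addition whose benefit cannot be sized from the documents; it only lets the slope differ between the 6- and 12-month changes.

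Grouped residual variance is a trade-off. With a common effect it gives no gain at equal SDs, about 83-84% power at a ratio near 2 and about 90% at 3. It moves the estimate towards the effect without diabetes. With an effect of −0.5 in diabetes and an SD of 1.0 there, power falls from 88.6% to 85.7%. It fits as a sensitivity analysis.

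**What to change.** Before database lock:

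1. In SAP section 5.6.2, always include baseline diabetes status (yes/no) as a fixed effect in the primary model, using the same definition as the section 6.6 subgroup, and say how missing status is handled.
2. Add baseline glucose by visit to the fixed effects.
3. Check the SD of change by baseline diabetes status with treatment arms blinded. Pre-specify, as a sensitivity analysis only, a model with residual variance by diabetes status (REPEATED with GROUP= in PROC MIXED). State that it gives participants with diabetes less weight and shifts the estimate towards the effect without diabetes.
4. Since section 5.7.2 reuses the primary model for the cardiometabolic factors, say whether the diabetes term carries over.

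The cost is SAP wording, two fixed-effect terms and one extra model run. Diabetes status is already collected, and no new data or participants are needed.

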### 5.1.2 Protocol deviations

So far identified protocol deviations are:

Main protocol deviation:

The main protocol deviation is lack of compliance to active or control therapy, for which assessment of 24-hour urine is the best indication. We will address this in per protocol analyses, please see details in section above (part 4.1).

Other protocol deviations:

\*Attendance at clinic study visit outside the predefined time windows. The time between visits summary statistics will be shown but will not result in any per protocol analyses.

\* Attendance at clinic study visit V3, V6 or V8 in a non-fasted state. These participants will be excluded from the per protocol analyses.

Thus, we will detail the numbers of subjects (total and per study treatment group) who had any protocol deviation for these respective reasons, or for other reasons not yet encountered.

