### 5.1.3 Populations

We expect a final study sample for intention to treat analysis of at least n=544 evaluable study subjects who have completed the protocol (i.e. with at least 2 fasting glucose measurements, meaning at V3 and at either V6 or V8 or at both V6 and V8). We expect a dysbalance in the final study sample (46% intervention vs 54% control therapy) due to dysbalance in the drop-out rate between intervention and control groups.

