### 5.7.2 Analysis of secondary outcome parameters

New-onset diabetes is defined as 2 consecutive fasting plasma glucose values  $\geq 7.0$  mmol/L or 2-hour post OGTT value of  $\geq 11.0$  mmol/L after the baseline exam (V3). In addition, new onset diabetes is considered present if diagnosed by a physician outside of the current study, as assessed in the questionnaire (answering yes on having had a physician diagnosis of diabetes or having been prescribed

medication for diabetes) after the baseline exam (V3). All individuals with a diagnosis of diabetes at or before the baseline exam (V3) will be excluded in the analysis of incidence of diabetes.

The difference in diabetes incidence between the intervention and control group will be analyzed using logistic regression with diabetes incidence as the binary outcome and treatment arm as exposure variable and reported as the odds ratio (OR) including 95 % CI for diabetes incidence in intervention vs control. As the randomization should lead to no difference in diabetes risk factors, the main analysis will only be adjusted for sex (as the randomization is stratified by sex, this covariate will be included in all outcome analyses), but we will also add a sensitivity analysis to adjust for key diabetes risk factors at baseline (fasting glucose, diabetes status, BMI, age), if there is a clinically significant difference in these factors between treatment groups despite the randomization.

Cardiometabolic risk factors will be analyzed using the same method as for the primary outcome, but with baseline value for the actual factor as a covariate instead of baseline value of fasting plasma glucose.

In addition, to assess the possible association between change in fasting plasma glucose levels, copeptin, other cardiometabolic risk factors, other blood laboratory parameters and urine laboratory parameters, we propose to analyze correlation(s) between delta value of outcome parameters and delta value of the efficacy parameters (e.g. urine volume, urine osmolality and plasma copeptin) with Pearson or Spearman correlation analyses.

- Outcome parameters are fasting plasma glucose and all secondary continuous outcome parameters listed in section 5.7.1 above.

We emphasize that in these correlation analyses, copeptin will be regarded both as an outcome parameter and as an efficacy parameter.

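### SAP 5.6.2: the exponential or AR(1) structure gives the 6- and 12-month glucose changes one common variance, so the 12-month primary test holds its 5% level only if the two residual SDs are equal

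*SAP*

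**What the plan says.** SAP 5.6.2 bases the main analysis on a PROC MIXED model for the change in fasting glucose at 6 and 12 months. Fixed effects are sex, baseline glucose, treatment, visit and treatment by visit. It reports "LS-means differences on the changes from baseline to 12 months and from baseline to 6 months in fasting plasma glucose". SAP 5.6.1 and 3.3 identify the 12-month change as the primary outcome.

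On the covariance the SAP says: "We will in the mixed regression analysis model within-patient correlation to decrease exponentially with number of days between measurements or through an AR(1) model". It adds: "The choice of correlation structure specifies the variance-covariance matrix in the mixed regression model". The reason given is: "The choice of covariance structure rests on principles of parsimony, simplicity and prior beliefs, rather than post-analysis testing". The SAP names no heterogeneous form, visit-specific variance or robust standard error. Residual plots will be inspected, but no action is stated if the spread differs by visit.

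The only SD of change observed in this trial is in SAP 7 (also in 3.3): "The pooled standard deviation of delta fasting plasma glucose (mmol/L) at month 12 is 0.58". No 6-month SD is given. SAP 5.7.2 carries the model over to other endpoints: "Cardiometabolic risk factors will be analyzed using the same method as for the primary outcome".

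**The concern.** AR(1) and exponential decay describe correlation. In their standard PROC MIXED form each has one residual variance for all visits. Because the model contains treatment by visit, the 12-month estimate is essentially the adjusted 12-month mean difference, but its standard error comes from a variance pooled over both visits.

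If residual glucose change varies less at 6 than at 12 months, the 12-month confidence interval is too narrow and the test rejects too often. If it varies more, the test is conservative and loses some power. The 5% level of the primary test therefore depends on an equality that nothing in the documents supports or refutes. The same holds for each continuous secondary outcome measured at both visits, each with its own unknown variance ratio.

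**Working it through.** **Inputs from the documents.** Two-sided 5% level (SAP 6.1); difference 0.14 mmol/L, SD of 12-month change 0.58, 544 evaluable subjects, 80% power (SAP 3.3); expected split 46% to 54%, about 250 and 294 (SAP 5.1.3).

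**The plan's own figure.** n per group = 2 x (1.960 + 0.842)^2 x 0.58^2 / 0.14^2, which rounds up to 270, as stated. With the 46/54 split the total is 543 (stated: 544), and power at 250 and 294 is 80.1%.

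**Effect of the common variance.** Let r be the residual SD at 6 months divided by that at 12 months. With complete data, the model standard error divided by the true one is k = sqrt((1 + r^2)/2), and the actual level is 2 x (1 - Phi(1.96 k)). The documents do not give r, so every value below is an assumption.

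| r | k | actual level |
|---|---|---|
| 0.80 | 0.9055 | 7.6% |
| 0.90 | 0.9513 | 6.2% |
| 0.95 | 0.9753 | 5.6% |
| 1.00 | 1.0000 | 5.0% |
| 1.05 | 1.0253 | 4.5% |
| 1.10 | 1.0512 | 3.9% |
| 1.20 | 1.1045 | 3.0% |

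**What could move r.** Suppose glucose has the same SD at every visit (assumed), and let a and b be the correlations of baseline with month 6 and month 12. After baseline adjustment, r = sqrt((1 - a^2)/(1 - b^2)). With a = 0.7 and b = 0.7, 0.65, 0.6 or 0.49, r is 1.00, 0.94, 0.89 or 0.82. The last case, b = 0.7^2, is pure exponential decay starting at baseline.

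**Simulation of the planned model.** REML with the planned fixed effects, 250 and 294 subjects, SD of 12-month change 0.58 in every cell, 3% of 6-month and 8% of 12-month values missing at random (assumed), 6,000 runs per cell, Monte Carlo error about 0.3 percentage points:

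| r | formula | common variance | unstructured |
|---|---|---|---|
| 1.000 | 5.0% | 5.3% | 5.5% |
| 0.940 | 5.7% | 5.9% | 5.2% |
| 0.893 | 6.3% | 6.4% | 4.8% |
| 0.819 | 7.3% | 6.7% | 4.7% |
| 1.1 | 3.9% | 4.0% | 5.2% |
| 1.2 | 3.0% | 3.0% | 5.2% |

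At r = 0.819 the common-variance model reports a mean standard error of 0.0409 against an empirical SD of 0.0441, about 7% too small (0.0409/0.0441 = 0.93). The unstructured model reports 0.0451 against 0.0444.

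**Price of the alternative.** At equal SDs the mean standard error is 0.0477 with either matrix. To see what is lost when actual visit days leave the model, data were generated under exact exponential decay (correlation 0.5 at 182.5 days, equal SDs of 0.5; 3,000 runs). The SD of the 12-month estimate was 0.04487 (exponential) and 0.04490 (unstructured) with visits inside the 14-day windows of Protocol Table 1. With 30% of visits up to 60 days off (assumed), it was 0.04477 and 0.04481.

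**The case against.** The strongest reply is that no error is demonstrated. The deciding ratio is not in the documents, every level other than 5.0% comes from an assumed value, and departures within 5% of equality move the level by only about half a point. Glucose is taken fasting on the same schedule at both visits with one named method, so there is no specific reason to expect a large difference. The route to r below 1 also extends decay back to raw baseline glucose with constant spread, whereas the SAP states decay only for the modelled changes. With a flat baseline correlation the ratio is 1.00. All of this stands, and it is why the point is minor.

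A second reply is that the structure is prespecified with a reason, and that residual plots or the log transform in SAP 6.2 could reveal or reduce unequal spread. The prespecification is only partial, because the SAP leaves two structures open, although no consequence of that choice is shown here. The plots lead to no stated action, and the SAP rules out choosing the structure by testing after the analysis. Parsimony carries little weight with two visits: an unstructured matrix has three parameters instead of two.

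A third reply is that the exponential form uses actual visit days, which could help because late or early visits stay in the analysis: "The time between visits summary statistics will be shown but will not result in any per protocol analyses". The visit-day simulation shows no measurable gain.

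Finally, a heterogeneous form such as ARH(1) is not excluded. It is not named either, and the statement that the correlation structure fixes the whole covariance matrix points to the common-variance reading.

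**Conclusion.** The concern holds as a minor point. As written, and in standard PROC MIXED form, the 12-month primary test keeps its 5% level only if the residual SDs at 6 and 12 months are equal. Over assumed ratios from 0.8 to 1.2 the level runs from 7.6% to 3.0%; within 5% of equality it is 5.6% to 4.5%. The mechanism is certain, but the direction and size in this trial are unknown, so inflation is not shown.

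No shortfall against 80% power is claimed. The 0.58 is unadjusted, baseline adjustment lowers it by an unknown amount, and the evaluable count also includes subjects without a 12-month value (SAP 5.1.3: "meaning at V3 and at either V6 or V8 or at both V6 and V8").

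The figures assume equal SDs in the two arms. For secondary outcomes the point applies only to those measured at both visits. HbA1c, for example, is scheduled in Protocol Table 1 only at baseline and 12 months, so no 6-month variance enters its analysis.

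**What to change.** Before analysis, replace the two-way choice in SAP 5.6.2 with one prespecified unstructured 2x2 covariance matrix for the 6- and 12-month changes (PROC MIXED, REPEATED statement, TYPE=UN). Apply it to the primary outcome and to continuous secondary outcomes measured at both visits. The exponential model in days can remain as a sensitivity analysis.

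As a wording alignment only, state in the 5.6.1 table and in 5.6.2 that the 12-month contrast is the sole confirmatory test and the 6-month contrast is supportive. This agrees with the opening sentence of 5.6.1 and with 3.3.

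The cost is SAP wording, one program option and one extra covariance parameter. It needs no further data or patients, and the simulations show no measurable loss of precision.
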